A prospective study with larger sample size is warranted to confirm that the percentage of tumoral CD8 cells at the time of treatment can determine responsiveness to anti-PD-1 therapy and whether combination therapy can convert tumors from CD8 low to CD8 high. We propose a prospective clinical study in which patients with varying advanced solid tumors will be assigned to 1 of 2 treatment arms based on the percentage of tumoral CD8 cells at the time of treatment. Participants who have a tumor with $\geq 15\%$ CD8 cells (classified as CD8 high) will receive nivolumab monotherapy, and participants who have a tumor with $< 15\%$ CD8 cells (classified as CD8 low) will receive ipilimumab in combination with nivolumab.

It is well recognized that immune infiltration varies across tumor types, and different tumor types may display a range of therapeutic sensitivities. Several ongoing studies are evaluating nivolumab treatment in various tumor types (BMS Nivolumab Studies). To better assess the feasibility of using percent of tumoral CD8 cells as a biomarker for selecting checkpoint inhibitor therapy and to gain more insight regarding the design of the trial, we examined CD8 cells in a set of 195 tumor samples from 10 different tumor types (Figure 7). For tumor types in which anti-PD-1 treatment has been approved, the classification of CD8 high tumor is consistent with the clinical benefit reported. The 15% cutoff was selected based on data from retrospective

studies and evaluation of responses to checkpoint inhibitors. This study will advance the field by providing a prospective classification of CD8 high versus CD8 low tumors at the time of treatment, based on response to nivolumab, and address the predictive value of the CD8 biomarker for selecting patients who can benefit from nivolumab with or without ipilimumab.

Figure 7: Percentage of Tumoral CD8 T Cells by Immunohistochemistry in Different Tumor Types

ADC = adenocarcinoma; CRC = colorectal cancer; GBM = glioblastoma multiforme; HCC = hepatocellular carcinoma; IHC = immunohistochemistry; MSI = microsatellite instable; MSS = microsatellite stable; RCC = renal cell carcinoma; SCC = squamous cell carcinoma.

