9 STATISTICAL CONSIDERATIONS

9.1 SAMPLE SIZE DETERMINATION

A total of up to approximately 200 participants with varying tumor types will be enrolled. Enrollment to initial biopsy may be about 10% higher (ie, approximately 220 participants) to account for unexpected challenges obtaining CD8 infiltration information. The selection of 200 participants is to have sufficient numbers in the CD8 high and CD8 low tumor groups in larger tumor populations to report subgroup response rates, the transformation from CD8 low to high, as well as to predict response from marker and clinical information. With 200 participants, approximately 40 and 160 participants are estimated for the CD8 high and CD8 low tumor groups, respectively (Figure 7). Clinical benefit rate (CBR) within tumor groups is expected to range from 10% to 30% (Nivolumab IB). An average CBR of 20% is assumed to provide approximately 32 participants with clinical benefit in the CD8 low tumor group. With 160 participants, a 95% credible interval of CBR with 32 responders would be (14.2%, 26.5%) assuming a beta(0.4, 1.6) prior. Similarly, if there are 30 participants in the largest disease subgroup, a 95% credible interval of response would be (8.3%, 35.2%) assuming 6 responders and a similar prior. There is no prior for the expected proportion of participants who will convert from CD8 low to CD8 high on treatment as this is a first look for this endpoint. The 95% credible interval for 16/160 (10%) participants converting would be (5.9%, 15.1%) and for 80/160 (50%) the credible interval would be (42.3%, 57.7%). Similarly, 8 of 40 participants are in the CD8 high group expected to exhibit benefit, resulting in a 95% credible interval of (9.5%, 33.2%). The selection of 200 participants allows a minimum reasonable number for estimating CBR in the CD8 high tumor group. For secondary analyses, if there are 20 responders in any CD8 status and/or tumor site group, it would be reasonable to perform multivariate logistic regression with 2 variables to predict response. Therefore, 200 participants is the smallest reasonable sample size for the initial exploration of efficacy prediction in this population.

Additional widths of credible intervals of CBR for possible subgroup sizes are presented in [Table 11](#).

Table 11: Possible Subgroup Sizes

Subgroup Size	Clinical Benefit Rate	Expected Success	95% Credible Interval
160	10	16	(6.0, 15.2)
125	10	12	(5.3, 15.5)
100	10	10	(5.1, 16.7)
75	10	8	(5.0, 18.7)

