9.4.1 Efficacy Analyses

The efficacy analysis will be based on the modified Intent-to-Treat (mITT) Population, which comprises all enrolled participants with sufficient biopsy results to be assigned to a treatment arm and who received at least one dose of study drug, unless otherwise specified. Participants will be analyzed according to the study intervention to which they were assigned.

The primary endpoint of CBR will be reported among all participants within each study intervention group with a 95% credible interval assuming a beta (0.4, 1.6) prior. Per RECIST, to

be assigned a best overall response of CR or PR, changes in tumor measurements must be confirmed by a repeat assessment that should be performed no less than 4 weeks after the criteria for response are first met. Participants who do not have a disease assessment will be counted as not having clinical benefit. In addition, CBR and similar credible intervals will be reported for each tumor site and study intervention subgroup that has at least 10 participants.

The proportion of participants whose tumors change from CD8 low to CD8 high expression will be reported with a 95% credible interval with no prior as this is the first look.

For secondary endpoints, baseline CD8 counts will be explored for association with CBR using logistic regression models and with OS using Cox regression models. Multivariate models will be explored with up to 1 variable for every 10 events. For CBR prediction, an event is an objective response (CR or PR or SD as defined above). For association with survival, an event is a participant death.

Among the On-treatment Biopsy Population, both the baseline and on-treatment biopsies will be associated with response and survival using similar logistic and Cox regression models described above, assuming there are sufficient events to carry out the regression analyses. The association of CD8 changes from baseline to on treatment with clinical outcomes will also be explored.

The exploratory endpoint of changes in PSA (absolute and percent) from baseline will be analyzed by cohort for advanced prostate cancer participants.

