### 5.4 Efficacy Analysis

The efficacy analysis will be based on the modified Intent-to-Treat (mITT) Population, which comprises all enrolled participants with sufficient biopsy results to be assigned to a treatment arm and who received at least one dose of study drug, unless otherwise specified. Participants will be analyzed according to the study intervention to which they were assigned.

This study is not intended or powered for hypothesis testing, including comparisons between study intervention groups. Due to the exploratory nature of this study, no control of type I error will be applied for any of the endpoints.

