#### 5.4.2.4 Association of CD8 with clinical outcomes

Several analyses will be performed to investigate the association between the percentage of CD8 cells and clinical outcomes.

- Among the participants who had tumors that converted from cold (CD8 <15%) at baseline to hot (CD8  $\geq$  15%) at any on-treatment biopsy, the following will be reported:
  - The number and proportion of patients who met ORR response criteria. A 95% credible interval will be estimated with no prior.
  - The number and proportion of patients who met CBR response criteria. A 95% credible interval will be estimated with no prior.
- Logistic regression models will be fit to assess the relationship between percentage of CD8 and clinical response (ORR and CBR). Each regression model will include an intercept term. P-values will be calculated using a Wald test to test whether the coefficient for the CD8 variable is significantly different from 0. See Table 3 for details about each regression model.

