**Table 3: Logistic Regression Model Parameters**

| Model number | Response variable (y) | Explanatory variable (x)                                                                              | Analysis Population            |
|--------------|-----------------------|-------------------------------------------------------------------------------------------------------|--------------------------------|
| 1            | CBR                   | Baseline percentage of CD8 cells                                                                      | mITT Population                |
| 2            | ORR                   | Baseline percentage of CD8 cells                                                                      | mITT Population                |
| 3            | CBR                   | Maximum percentage of CD8 cells across all on-treatment biopsies                                      | On-treatment Biopsy Population |
| 4            | ORR                   | Maximum percentage of CD8 calls across all on-treatment biopsies                                      | On-treatment Biopsy Population |
| 5            | CBR                   | Absolute change between baseline and maximum percentage of CD8 cells across all on-treatment biopsies | On-treatment Biopsy Population |
| 6            | ORR                   | Absolute change between baseline and maximum percentage of CD8 cells across all on-treatment biopsies | On-treatment Biopsy Population |
| 7            | CBR                   | CD8 Conversion Flag
(1 = CD8 converter, 0 = non-converter)                                         | On-treatment Biopsy Population |
| 8            | ORR                   | CD8 Conversion Flag
(1 = CD8 converter, 0 = non-converter)                                         | On-treatment Biopsy Population |

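### In the metastatic portion, SAP Table 3 pools single-variable CD8 models over about 19 tumor types, so a difference between tumor types can be reported as a CD8 association

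*SAP*

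**What the plan says.** SAP 5.4.2.4: "Logistic regression models will be fit to assess the relationship between percentage of CD8 and clinical response (ORR and CBR". It adds that "Each regression model will include an intercept term" and that "P-values will be calculated using a Wald test to test whether the coefficient for the CD8 variable is significantly different from 0". Table 3 lists eight models with one explanatory variable each. For models 1 and 2 it is "Baseline percentage of CD8 cells", fitted in the whole mITT population. Models 3 to 8 use the maximum on-treatment CD8, its change from baseline, or a conversion flag, in the On-treatment Biopsy Population. No model has tumor type as a covariate, stratum or random effect.

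On tumor type, Protocol 2.2.2 says: "It is well recognized that immune infiltration varies across tumor types, and different tumor types may display a range of therapeutic sensitivities". It also says that, across types with an approved anti-PD-1 treatment, CD8-high classification agrees with the benefit reported. Protocol 9.1: "Clinical benefit rate (CBR) within tumor groups is expected to range from 10% to 30" (percent). Inclusion criterion 4 lists 19 types under Amendment 2; earlier enrollment was not limited to that list.

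On modeling, Protocol 9.4.1 says: "Multivariate models will be explored with up to 1 variable for every 10 events". SAP Section 2 says the SAP supersedes the protocol's analysis plan. SAP Section 6 says the baseline CD8 association with CBR and OS has been removed.

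**The concern.** The study's stated aim is the predictive value of CD8 for selecting patients. If inflamed tumor types both carry more CD8 cells and respond more often, a pooled model shows a CD8 coefficient even when CD8 says nothing among patients with the same histology. A marker that only separates histologies adds nothing to the diagnosis already on file, and a single-variable pooled model cannot tell the two situations apart.

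This is a separate matter from CD8 determining the regimen. Fitting the models inside one arm would deal with regimen but would leave tumor type mixed with CD8. The factor needed to deal with it, cancer location, is already among the SAP's baseline variables (5.3).

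**Working it through.** **Plan figures reproduced.** The documents give no operating characteristics for the Table 3 models, so I checked the figures that carry the sample size and CBR. With the beta(0.4, 1.6) prior, 32/160 has posterior beta(32.4, 129.6) and 95% interval (14.2%, 26.5%); 8/40 has beta(8.4, 33.6) and (9.5%, 33.2%). Both match Protocol 9.1. Expected benefit events: 32 + 8 = 40 in 200.

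**Mechanism by hand.** Put half the participants in types with CBR 10% and 10% CD8 high, and half in types with CBR 30% and 30% CD8 high, with no CD8 effect inside either half.
- CD8 high overall: 0.5×0.1 + 0.5×0.3 = 20%, which is the plan's 40 of 200.
- CBR in CD8 high: (0.5×0.1×0.1 + 0.5×0.3×0.3)/0.20 = 25.0%.
- CBR in CD8 low: (0.5×0.9×0.1 + 0.5×0.7×0.3)/0.80 = 18.75%.
- Pooled odds ratio: (0.25/0.75)/(0.1875/0.8125) = 1.44. The true within-type value is 1.00.

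**Simulation of model 1.**
- From the documents: N = 200, 19 types, CBR from 10% to 30%, 20% of tumors CD8 high.
- Assumed: equally likely types, evenly spaced CBR, log-normal CD8, two-sided 0.05, no regimen effect, no CD8 effect inside any type.
- Varied because Figure 7 is not available to me: the share of log-CD8 variance lying between types (10%, 30%, 50%) and the correlation of type-level CD8 with type-level CBR (0, 0.5, 0.9).

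There were 3,000 runs per setting. The simulation error is about √(0.05×0.95/3000) = 0.4 percentage points near 5%. The odds ratios are large-sample values from a separate simulation.

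| Variance between types | Correlation | Pooled p<0.05 | Stratified by type p<0.05 | Pooled OR per SD of CD8 |
|---|---|---|---|---|
| 10% | 0 | 3.8% | 4.9% | 1.00 |
| 10% | 0.5 | 6.1% | 5.0% | 1.04 |
| 10% | 0.9 | 8.0% | 5.4% | 1.08 |
| 30% | 0 | 4.8% | 4.7% | 1.00 |
| 30% | 0.5 | 7.4% | 5.5% | 1.08 |
| 30% | 0.9 | 13.1% | 4.4% | 1.14 |
| 50% | 0 | 4.4% | 4.7% | 1.00 |
| 50% | 0.5 | 9.5% | 4.6% | 1.10 |
| 50% | 0.9 | 20.0% | 3.9% | 1.19 |

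The type-adjusted odds ratio was 0.98 to 1.01 throughout.

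**Which adjustment works.**
- The protocol's rule allows 40/10 = 4 variables. CD8 plus 18 type indicators is 19 variables and would need 190 events.
- Collapsing 19 types arbitrarily into four groups still left 11% or more at correlation 0.9 with 30% to 50% of the variance between types, against 13% to 20% pooled.
- The 40 events apply only to CBR in all 200 mITT participants. ORR leaves out stable disease, and models 3 to 8 use a smaller population, so both have fewer events.

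**The case against.** The strongest reply is that the SAP presents these as exploratory associations. It says the study is not powered for hypothesis testing and that "no control of type I error will be applied for any of the endpoints". An unadjusted association is a legitimate summary on those terms, and SAP 5.4.4 allows CBR, ORR and conversion to be shown by tumor type. This stands in part: the unadjusted models may stay. But waiving type I error control deals with how often p-values mislead by chance, whereas confounding shifts the estimate itself. The subgroup displays cover rates, not the CD8 association.

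Three stronger readings are tempting, and the documents do not support them.
- A reader might infer that the models *will* report a spurious association with a small p-value. Bias needs type-level CD8 and benefit to move together, and Protocol 2.2.2 says only that sensitivities may differ. Even at correlation 0.9, 80% or more of the simulated trials did not reach p<0.05. Steeper results are possible: three equal groups with CD8 and CBR in perfect order (CBR 10/20/30%, median CD8 4/7/12%) gave about 17%. That is close to a worst case, and its CD8 medians are not in the documents.
- A reader might infer that the SAP dropped a planned tumor-type adjustment. Protocol 9.4.1 names no covariate, and the two-variable model in 9.1 is conditional on 20 responders and could be fitted inside one tumor site.
- A reader might extend the point to the prostate portion. SAP 3.4 analyzes that portion independently, and it has a single histology.

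**Conclusion.** The point holds for the metastatic portion, with *can* rather than *will*. At the protocol's own 10% to 30% CBR range, with no CD8 effect inside any type, the pooled model 1 test is positive in about 4% to 20% of trials, with a pooled odds ratio of 1.00 to 1.19 per SD of CD8. Stratified by tumor type, the rate is about 5%. The size rests on the assumed between-type CD8 variance and its correlation with CBR. It was computed for model 1 only; models 2 to 8 share the structure but have no figure here. That the models pool tumor types is read from Table 3, which names whole populations and no stratum.

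Two statements in SAP Section 6 need correcting in any case. It says the baseline CD8 association with CBR will not be analyzed, while Table 3 model 1 is that analysis. It also does not mention that the protocol's multivariate models are gone. Their loss might be read into the removal of the baseline analysis, but Protocol 9.4.1 planned similar models for the on-treatment biopsies too.

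**What to change.** For the metastatic portion, add to SAP 5.4.2.4 that each Table 3 model is also fitted stratified by tumor type. Use conditional logistic regression, or CD8 centered within tumor type with a random intercept. A random intercept without centering mixes within-type and between-type information. Do not use 18 fixed effects or arbitrarily collapsed groups. Define the strata before database lock, because some listed types overlap (gynecologic malignancies beside cervical and ovarian).

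Report the within-type odds ratio and interval beside the unadjusted one, and label the unadjusted one as not separating CD8 from histology. In Section 6, reconcile the removal statement with model 1 and list the loss of the multivariate models.

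The cost is a table edit, modest programming and somewhat wider intervals. Types with no events, or only events, contribute nothing to the conditional estimate. With equal type sizes (200/19 = 10.5 participants), a type with CBR 10% has no events with probability 0.9^10.5 = 33%, and one with CBR 30% with probability 0.7^10.5 = 2%. The ORR and on-treatment models will lose more, so the number of informative types and events should be shown with each result.

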50	10	5	(3.7, 19.9)
40	10	4	(3.2, 21.2)
30	10	3	(2.6, 23.2)
160	20	32	(14.2, 26.5)
125	20	25	(13.5, 27.4)
100	20	20	(12.9, 28.3)
75	20	15	(11.9, 29.6)
50	20	10	(10.4, 31.8)
40	20	8	(9.5, 33.2)
30	20	6	(8.3, 35.2)
160	30	48	(23.1, 37.1)
125	30	38	(22.6, 38.5)
100	30	30	(21.4, 39.0)
75	30	22	(19.6, 39.6)
50	30	15	(18.1, 42.6)
40	30	12	(16.9, 44.0)
30	30	9	(15.2, 46.0)

A total of approximately 20 advanced prostate cancer participants with CD8 low tumors will be treated with the combination of nivolumab and ipilimumab, in 1 of 2 dosing cohorts. The first 10 participants enrolled will be randomly allocated by the Sponsor into one of two cohorts (5 participants per cohort) to evaluate the safety of different dose levels of ipilimumab in combination with nivolumab. If the higher dose level (ipilimumab 5 mg/kg + nivolumab 1 mg/kg) is determined to be tolerable per [Section 6.6.1.4](#), an additional 10 participants will be enrolled at this higher dose level (Prostate Cohort B). If the safety profile of Prostate Cohort B is deemed unacceptable, an additional 10 participants will be enrolled at the lower dose level (Prostate Cohort A).

We hypothesize that higher doses of ipilimumab will demonstrate a larger proportion of participants who convert from CD8 low to CD8 high. There is no prior for the expected proportion of participants who will convert from CD8 low to CD8 high at the various dose levels of ipilimumab. With 15 participants enrolled in Prostate Cohort B, Table 12 provides 95% credible intervals for possible CD8 conversion rates in the cohort. For example, a 95% credible interval assuming 6/15 (40%) participants converting in the cohort would be (17.7%, 64.9%).

Table 12: Credible Intervals for CD8 Conversion

Subgroup Size	CD8 Conversion Rate	Expected Successes	95% Credible Interval
15	20	3	(4.7, 42.8)
15	40	6	(17.7, 64.9)
15	60	9	(35.1, 82.3)

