### 3.4 Analysis Timing

Analysis for the Advanced Metastatic Cancer and Advanced Prostate Cancer portions will be performed independently and at different times due to differences in enrollment timelines.

The analysis of complete data for the clinical study report (CSR), described in the main body of this document, will be performed after all participants have been followed for at least 9 months or have discontinued early from the study, and all data from the study through the clinical cutoff date have been entered and reviewed for completeness.

Analysis of efficacy and safety endpoint may be performed prior to the CSR analysis. These results may be presented and/or published prior to the CSR analysis.

The study will formally end once all participants have either completed the safety and survival follow-up periods or have discontinued early from the study, all data from the study are entered in the clinical database, and the clinical database is locked.

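### In the separately analysed prostate portion, the Wald p-value for Models 7 and 8 falls near 1 whenever a cell is empty, however strong the association

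*SAP*

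**What the plan says.** SAP 5.4.2.4 sets out logistic regressions of CBR and ORR on CD8 and fixes the test for all of them: "P-values will be calculated using a Wald test", applied to the CD8 coefficient in each model. Table 3 lists eight single-covariate models. Models 1-6 use a continuous CD8 measure. Models 7 and 8 use the "CD8 Conversion Flag", coded "1 = CD8 converter, 0 = non-converter", in the On-treatment Biopsy Population. The SAP has no rule for zero cells, separation, non-convergence or a minimum number of events.

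SAP 3.4 separates the two parts of the study: "Analysis for the Advanced Metastatic Cancer and Advanced Prostate Cancer portions will be performed independently". On size, Protocol 9.1 says: "A total of approximately 20 advanced prostate cancer participants with CD8 low tumors will be treated with the combination". It bases its Table 12 on "With 15 participants enrolled in Prostate Cohort B", whereas SAP Section 3 has 10 per arm. On-treatment biopsies in this portion are required only where medically feasible (Protocol 4.1.1), so the number available to Models 3-8 can be lower. Neither document says whether the models are fitted per prostate cohort or for the prostate portion as a whole.

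**The concern.** The Wald statistic is the estimated log-odds ratio divided by its standard error. When one cell of the 2x2 table is empty, the maximum-likelihood estimate is infinite. The fitted value then depends on where the software stops iterating, its standard error grows much faster than the estimate, and the ratio falls towards zero. The printed p-value reflects the stopping rule rather than the evidence.

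This matters most when every participant who benefits is a converter. That is the pattern the study's rationale points towards, and the association of CD8 infiltration with clinical outcome is a stated secondary objective. A printed p of 0.999 beside such a table would be read as no association.

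**Working it through.** **Inputs.** n=20 (prostate CD8-low, both cohorts) and n=15 (Cohort B), from Protocol 9.1. CBR 10-30%, average 20%, is the Protocol 9.1 range across tumor groups. Conversion of 20%, 40% and 60% comes from the Table 12 illustrations. Applying these rates to prostate cancer is an assumption. The contrast of 50% benefit in converters with 5% in others is also assumed. The 0.05 level is only a yardstick, since the SAP sets no alpha.

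**The plan's own figure.** Table 12 gives (17.7%, 64.9%) for 6/15. The 2.5% and 97.5% quantiles of Beta(6, 9), that is Beta(x, n-x) with no prior, are 17.7% and 64.9%. The rows for 3/15 and 9/15 also match.

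**One table.** 4 of 6 converters and 0 of 14 non-converters benefit.
- Likelihood ratio: the fitted log-likelihood is 4 ln(4/6) + 2 ln(2/6) + 0 = -3.819. The null value is 4 ln(0.2) + 16 ln(0.8) = -10.008. Twice the difference is 12.38 on 1 df, p=0.0004.
- Fisher: C(6,4)/C(20,4) = 15/4845, p=0.003.
- Wald: standard error about 13,000, p=0.999.

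**Further tables at n=15** (converters with/without benefit; non-converters with/without):

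| Table | Wald | LR | Fisher | Firth |
|---|---|---|---|---|
| 3/3; 0/9 | 0.998 | 0.010 | 0.044 | 0.027 |
| 4/2; 0/9 | 0.998 | 0.002 | 0.011 | 0.006 |
| 6/0; 0/9 | 0.9997 | <0.0001 | 0.0002 | 0.0001 |
| 5/1; 1/8 (no zero cell) | 0.016 | 0.004 | 0.011 | not run |

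The later decimals of the first three Wald values vary with the software's stopping rule. Without a zero cell, Wald behaves normally.

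**How often a cell is empty.** With cell probabilities p, the chance that a given cell is empty is (1-p)^n; overlaps are subtracted. For n=20, conversion 40%, benefit 50% vs 5%, the cells are 0.20, 0.20, 0.03 and 0.57. So 2(0.80^20) + 0.97^20 - 2(0.77^20) = 0.023 + 0.544 - 0.011 = 0.556. Over conversion 20-40%, by exact enumeration:

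| Benefit 50% vs 5% | n=20 | n=15 |
|---|---|---|
| Any zero cell | 53-58% | 66-73% |
| Zero cell and Fisher p<=0.05 | 29-39% | 23-32% |
| Share of Fisher p<=0.05 tables with a zero cell | about 70% | about 90% |

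**With no association**, CBR 20% and conversion 20-40%, a zero cell occurs in 26-48% of tables at n=20 and 40-62% at n=15. At n=20 and conversion 20%, 42 of the 48 percentage points are tables in which no converter benefits, and only 0.7 points have Fisher p<=0.05. In the most favourable corner (n=20, CBR 30%, conversion 40-60%) the zero-cell chance is 10%.

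**Models 1-6.** With no association and a continuous covariate, complete separation has probability 2 x sum over k=1..n-1 of r^k(1-r)^(n-k), where r is the response rate. At n=15 this is 2.3% for r=20% and 5.1% for r=10%. When it happens the fault is the same: a covariate that separates 3 responders of 15 gave Wald p=0.9997 and LR p=0.0001.

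**The metastatic CD8-low group (n=160).** The zero-cell chance is 0.15% at conversion 20% and CBR 20%, 4% at 10% and 20%, and 20% at 10% and 10%.

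**The case against.** SAP 5.4 says the study is neither intended nor powered for hypothesis testing, and no decision uses these p-values. SAP 5.4.2.4 also reports ORR and CBR among converters with credible intervals, so four benefits in six converters would be visible. That stands and limits the stakes. However, no matching summary is planned for non-converters, and the Wald p-value would still be printed for a secondary objective.

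Protocol 9.4.1 makes the on-treatment regressions conditional on there being enough events. At 20% CBR, 20 participants give 4 events, so the prostate models might not be run. The SAP neither repeats that condition nor lists it as removed in Section 6, and neither document gives a threshold. This weakens the point without removing it.

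The analysis sample is also uncertain. The On-treatment Biopsy Population is not restricted to CD8-low tumors, so prostate CD8-high participants could enter as non-converters and fill an empty cell. Missing biopsies act in the opposite direction.

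Two stronger readings are tempting. A reader might infer that all eight models break down in the prostate portion. Zero cells arise only in Models 7 and 8, and separation in Models 1-6 is uncommon with no association. A reader might also take the 26-62% zero-cell frequency under no association as the rate at which strong associations are hidden. It is not: few of those tables show a strong association, and some have an empty margin, so that no method can estimate a coefficient.

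**Conclusion.** The point holds for Models 7 and 8 in the prostate portion. The prescribed test gives p near 1 for any table with a zero cell, including perfect separation. If conversion really does mark benefit as strongly as 50% vs 5%, the plan would misreport about 70% (n=20) to 90% (n=15) of the tables that Fisher's test would call clear.

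That failure of the test is certain; its frequency is not. It rests on assumed prostate benefit and conversion rates and on how many participants have usable biopsies. A reader might infer that the trial would reach a wrong conclusion about CD8. The documents do not support that, because no stopping rule, cohort decision or confirmatory claim depends on these p-values. The consequence is a misleading reported p-value for a secondary, exploratory analysis.

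**What to change.** In SAP 5.4.2.4, replace the Wald sentence. For Models 7 and 8, use Fisher's exact test or a Firth-penalised logistic model with a profile-penalised-likelihood test. For Models 1-6, use likelihood-ratio or Firth tests, so that separation is handled in the same way throughout. A plain likelihood-ratio test is less suitable for Models 7 and 8: with no association at n=20 (conversion 40%, CBR 20%), zero-cell tables with LR p<=0.05 already make up 6.3% of all tables, against 1.1% for Fisher. Where a margin is empty, report the counts and state that no coefficient can be estimated.

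The same edit should say whether the models are fitted per prostate cohort or for the whole portion, and whether the protocol's condition on sufficient events still applies.

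The cost is one sentence and a standard software option, with no new data. In the metastatic group Models 7 and 8 will seldom meet a zero cell unless conversion and benefit are both near 10%.
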